APPENDIX B: CLINICAL LABORATORY ANALYTES

Standard Safety Chemistry Panel

Alanine aminotransferase Albumin
Alkaline phosphatase Amylase
Aspartate aminotransferase Bicarbonate
Blood urea nitrogen Calcium

Chloride Creatine kinase

Creatinine Estimated glomerular filtration rate [1]

Gamma-glutamyl transferase Glucose (fasting)

Glycosylated hemoglobin [2] High-sensitivity C-reactive protein

Inorganic phosphorus Lactate dehydrogenase

Lipase Potassium
Sodium Total bilirubin
Total protein Uric acid

- Calculated using the Chronic Kidney Disease Epidemiology Collaboration equation. (Source: CKD-EPI equations for glomerular filtration rate [GFR]. MDCalc. https://www.mdcalc.com/ckd-epi-equations-glomerular-filtration-rate-gfr. Accessed 19 November 2021.)
- Screening Visit only.

Endocrinology

Follicle-stimulating hormone [1]

 A follicle-stimulating hormone test will be performed in women <55 years of age for whom it has been ≥1 year since their last menstrual period.

Hematology

Hematocrit Hemoglobin

Platelets Red blood cell count

White blood cell count and differential [1]

 Manual microscopic review is performed only if white blood cell count and/or differential values are out of reference range.

Pregnancy Test

Urine [1]

1. For women of childbearing potential only.

Lipid Profile

Apolipoprotein B
High-density lipoprotein-ApoE [1]
Low-density lipoprotein cholesterol [2]
Triglycerides

Apolipoprotein E (ApoE) High-density lipoprotein cholesterol Non-high-density lipoprotein cholesterol Very low-density lipoprotein cholesterol

- 1. With and without apolipoprotein C3.
- 2. Calculated using the Friedewald equation unless triglycerides (TGs) ≥400 mg/dL or low-density lipoprotein cholesterol (LDL-C) ≤50 mg/dL. If TG ≥400 mg/dL or LDL-C ≤50 mg/dL, then LDL-C level will be measured directly by preparative ultracentrifugation, also referred to as beta quantification. (Source: LDL calculated. MDCalc. https://www.mdcalc.com/ldl-calculated. Accessed 19 November 2021.) In addition, for all participants, LDL-C will be measured by preparative ultracentrifugation, also referred to as beta quantification, at Baseline (Day 1; Visit 2) and at the end of the 8-week Treatment Period (Day 56; Visit 5).

1 INTRODUCTION

The purpose of this Statistical Analysis Plan (SAP) is to provide a description of the statistical methods to be implemented for the analysis of data from NewAmsterdam Pharma BV Protocol TA-8995-203. The SAP will be finalized prior to database lock. Any deviations from the SAP after database lock will be documented in the final Clinical Study Report (CSR).

2 STUDY OVERVIEW

2.1 Study Objectives

2.1.1 *Primary Objective*

The primary objective of this study is to evaluate the efficacy of obicetrapib, compared to placebo, in reducing serum low density lipoprotein cholesterol (LDL-C) measured at Day 56 (Visit 5) when taken as an adjunct to a pre-existing stable statin therapy regime.

2.1.2 *Secondary Objectives*

The secondary objectives of this study include the following:

- To evaluate the effect of obicetrapib, compared to placebo, on serum apolipoprotein B (ApoB), non-high-density lipoprotein cholesterol (non-HDL-C), and high density lipoprotein cholesterol (HDL-C) concentrations at Day 56 (Visit 5), when taken as an adjunct to pre-existing stable statin therapy;
- To assess the mean plasma levels of obicetrapib at steady state on Day 56 (Visit 5) and Day 84 (Visit 6); and
- To evaluate the safety and tolerability profile of obicetrapib in Japanese subjects.

2.2 Study Design

2.2.1 *Overview*

The population for this study includes Japanese men and women, 18 to 75 years of age, inclusive, with a body mass index <35 kg/m², fasting LDL-C levels >70 mg/dL, and triglyceride levels <400 mg/dL at the Screening Visit, who are currently receiving stable statin therapy.

This study will be a placebo-controlled, double-blind, randomized, Phase 2 dose-finding study to evaluate the efficacy, safety, and tolerability of obicetrapib as an adjunct to stable statin therapy in Japanese participants. This study will take place at approximately 10 sites in Japan.

The total duration for the double-blind period for each subject will be up to 14 weeks, including up to 2 weeks for Screening, 8 weeks for blinded study treatment, and 4 weeks for safety follow-up. Please refer to Appendix A (Schedule of Procedures) of the study protocol for details.

At the Screening Visit (Visit 1), and up to 2 weeks before the start of the treatment period, participants will be required to sign an informed consent form (ICF) before any study-related procedures are performed. After signing the ICF, participants will be assessed for study eligibility.

Up to 2 weeks after the Screening Visit, participants will return to the site on Day 1 (Visit 2) and confirm study eligibility before being randomized and beginning treatment. Approximately 100

eligible participants (25 participants per treatment group) will be randomized in a 1:1:1:1 ratio to 1 of the following treatment groups:

- 2.5 mg obicetrapib (one 2.5 mg obicetrapib tablet);
- 5 mg obicetrapib (one 5 mg obicetrapib tablet);
- 10 mg obicetrapib (one 10 mg obicetrapib tablet); or
- Placebo (1 placebo tablet).

During the 8-week Treatment Period, the assigned study drugs will be administered by the participants orally once daily from Day 1 (Visit 2) to Day 56 (Visit 5). Participants will return to the site on Day 14 (Visit 3), Day 28 (Visit 4), and Day 56 (Visit 5) for efficacy, safety, and Pharmacokinetics (PK) assessments. Participants, Investigators, the Clinical Research Organization (CRO), and the Sponsor will be blinded to all lipid results from Day 1 (Visit 2) for the first participant and continuing to database lock in order to protect blinding to treatment assignment.

Participants will return to the site for a Safety Follow-up Visit on Day 84 (Visit 6), approximately 4 weeks after the end of the Treatment Period, for final safety and PK assessments.

Coronavirus Disease 2019 Contingency Measures

In cases of COVID-19 limitations, it is the Investigator's responsibility to assure the safety of participants. If investigators need to implement contingency measures, the investigators will communicate with the Sponsor and discuss the best practice with the sponsor. In the absence of a COVID-19 impact, it is expected that Investigators and participants follow the protocol requirements as set forth.

2.2.2 *Randomization and Blinding*

Participants who meet all eligibility criteria will be randomized into the study. Participants will be randomized in a 1:1:1:1 ratio to the 2.5 mg obicetrapib, 5 mg obicetrapib, 10 mg obicetrapib, or placebo treatment groups. At randomization, participants will be stratified according to their Screening Visit (Visit 1) LDL-C level (≥ 100 or < 100 mg/dL). An automated interactive response technology (IRT) system will be used to assign the participant to 1 of the 4 treatment groups, and visits will be registered in the IRT for Screening and Visits 1 through 5 as well as Early Termination, if applicable.

Participants, Investigators, the CRO, and the Sponsor will be blinded to all lipid results from Day 1 (Visit 2) for the first participant and continuing to database lock in order to protect blinding to treatment assignment.

2.2.3 *Study Drug*

The study drugs to be used in this study include the following:

- 2.5 mg obicetrapib tablet;
- 5 mg obicetrapib tablet;
- 10 mg obicetrapib tablet; and
- Matching placebo tablet.

The study drugs listed above will be packaged to provide doses of 2.5 mg, 5 mg, 10 mg obicetrapib, or placebo only. Placebo tablets will be visually identical. Participants will be randomized to receive 1 of the 3 doses of obicetrapib or placebo only. One tablet of study drug will be administered by the participant orally once daily from Day 1 (Visit 2) to Day 56 (Visit 5) at approximately the same time each morning.

2.2.4 *Sample Size Determination*

A sample size of at least 100 evaluable participants (i.e., 25 participants per treatment group) will provide $>90\%$ power to detect a 30% difference in LDL-C reduction at Day 56 (standard deviation (SD) of 25%) for each of the obicetrapib groups compared to the placebo group at a 2-sided significance level of 0.05.

The sample size for this study was determined in order to provide sufficient power for the analyses of the primary efficacy endpoint described in Section 3.4. Therefore, assuming a dropout rate of approximately 7%, an estimated enrollment target of approximately 108 participants (i.e., 27 participants per treatment group) is planned for this study. This sample size will also contribute sufficient participant exposure and safety data.

Participants will be stratified according to their Screening Visit (Visit 1) LDL-C levels (≥ 100 or < 100 mg/dL).

2.3 Study Endpoints

2.3.1 Primary Efficacy Endpoint

The primary efficacy endpoint is the percent change from Day 1 to Day 56 in LDL-C for each obicetrapib group compared to the placebo group.

2.3.2 Secondary Efficacy Endpoints

The key secondary efficacy endpoints include the following:

- Percent change from Day 1 to Day 56 in ApoB for each obicetrapib group compared to the placebo group;
- Percent change from Day 1 to Day 56 in non-HDL-C for each obicetrapib group compared to the placebo group; and
- Percent change from Day 1 to Day 56 in HDL-C for each obicetrapib group compared to the placebo group.

2.3.3 Safety Endpoints

The safety and tolerability profile of obicetrapib will be assessed by clinical laboratory assessments (chemistry and hematology), vital signs, physical examinations, and the incidence of adverse events and events of special interest (ESIs).

3 STATISTICAL METHODOLOGY

3.1 General Considerations

3.1.1 Analysis Day

Analysis day will be calculated from the date of first dose of study drug. The day of the first dose of study drug will be Day 1, and the day immediately before Day 1 will be Day -1. There will be no Day 0.

3.1.2 Analysis Visits

Scheduled visits will be assigned to analysis visits as recorded on the case report form (CRF). Early termination visits will be assigned to analysis visits according to the following visit windows:

Analysis Visit	Target Analysis Day	Low Analysis Day	High Analysis Day
Day 1	1	NA	NA
Week 2	14	2	21
Week 4	28	22	42
Week 8	56	43	70
Safety Follow-up	84	71	

Unscheduled visits recorded on the CRF will not be re-assigned and remain labeled as unscheduled.

3.1.3 *Definition of Baseline*

Unless otherwise stated, Baseline will be defined as the last measurement prior to the first dose of study drug.

3.1.4 *Summary Statistics*

Categorical data will generally be summarized with counts and percentages of participants. The denominator used for the percentage calculation will be clearly defined. Continuous data will generally be summarized with descriptive statistics including n (number of non-missing values), mean, median, standard deviation, minimum, and maximum.

3.1.5 *Evaluation of Site Effect*

This is a multi-center study. Sites will not be pooled for any planned inferential analysis but may be pooled for subgroup analysis to assess the heterogeneity of treatment effects among pooled sites. The final pooling algorithm, if needed, will be specified before treatment unblinding and will be provided as an addendum to the SAP. Additionally, a review of by-site effects will be performed in the context of data listing review.

3.1.6 *Handling of Dropouts and Missing Data*

Date Values

In cases of incomplete dates (e.g. adverse event (AE), concomitant medication, and medical history start and/or stop dates), the missing component(s) will be assumed as the most conservative value possible. For example, if the start date is incomplete, the first day of the month will be imputed for the missing day and January will be imputed for the missing month. If a stop date is incomplete, the last day of the month will be imputed for the missing day and December will be imputed for the missing month. Incomplete start and stop dates will be listed as collected without imputation.

Date imputation will only be used for computational purposes such as treatment-emergent status. Actual data values, as they appear in the original CRFs, will be presented within the data listings.

Non-Date Values

For sensitivity analyses of the primary efficacy endpoint, missing values will be imputed using multiple imputation (see Section 3.4.1). For the analyses of secondary and exploratory efficacy endpoints, no imputation will be made for missing values. Safety data will be used according to availability, with no imputation for missing data.

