3.7.1 Adverse Events (AEs)

AEs will be categorized by primary system organ class and preferred term as coded using the MedDRA (with the version specified in Data Management Plan) category designations.

Treatment-emergent adverse events (TEAEs) are defined as AEs that start after the first dose of study drug.

Adverse events of special interest will be flagged in CRF.

An overview of AEs will be provided including counts and percentages of participants (and event counts) by treatment and in total with the following:

- Any TEAEs overall and by maximum severity
- Any study drug related TEAEs overall and by maximum severity
- Any TEAEs of special interest
- Any treatment-emergent serious AEs (TESAEs)
- Any study drug related TESAEs
- Any TEAEs leading to discontinuation of study drug
- Any AEs leading to death

Counts and percentages of participants (and event counts) will also be presented by system organ class and preferred term for each of the categories in the overview.

Listings will be presented specifically for TEAEs, TESAEs, TEAEs leading to discontinuation of study drug, and TEAEs of special interest.

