3.7.6 Events of Special Interest

Liver-associated enzymes and total bilirubin will be summarized by the value and change from Baseline in the value, by treatment group and visit. In addition, the number and percent of participants with abnormal values for ALT, AST, and total bilirubin will be summarized. These summaries of participants with abnormal values will be performed overall; by normal Baseline; and by abnormal Baseline for ALT, AST, and total bilirubin individually. Hy's Law criteria ($>3 \times$ ULN for either ALT or AST, with accompanying total bilirubin $>2 \times$ ULN) will also be applied to the data. Any potential Hy's Law cases will be listed separately.

Muscle-related abnormalities will be summarized by treatment group. CK levels will be summarized by the value and change from Baseline in value, by treatment group and visit. In addition, the number and percent of participants with abnormal CK values will be summarized. These summaries of participants with abnormal CK values will be performed overall, by normal Baseline CK, and by abnormal Baseline CK.

Cases of NODM will be recorded and summarized using the appropriate system organ class. These events will be summarized by severity and relationship to study drug for each treatment group. Fasting plasma glucose and HbA1c will be monitored as specified in Appendix A (Schedule of Procedures) of the study protocol.

Baseline eGFR will be summarized by treatment group for actual value and for Baseline eGFR categories. Shift tables of eGFR category from Baseline to End of Treatment (EOT) will be provided by treatment group. Shift tables of urine albumin-creatinine ratio and urine protein creatinine ratio from Baseline to EOT will be provided by treatment group. Values of CK from Baseline to EOT will be summarized by treatment group and by Baseline eGFR category. Muscle related abnormalities will be summarized by treatment group and by Baseline eGFR category.

Cases of macular degeneration will be recorded and summarized using the appropriate system organ class. These events will be summarized by severity and relationship to study drug for each treatment group.

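### Post-dose AEs with a partial start date in the month (day missing) or year (day and month missing) of first dose are imputed to on or before first dose and lose TEAE status

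*SAP*

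**What the plan says.** SAP 3.1.6 (Handling of Dropouts and Missing Data, Date Values) covers incomplete AE, concomitant medication and medical history dates together. Its principle is that "the missing component(s) will be assumed as the most conservative value possible". The start-date rule follows as an example: "if the start date is incomplete, the first day of the month will be imputed for the missing day". An unknown start month is likewise set to January. The section then says what the imputed dates are for: "Date imputation will only be used for computational purposes such as treatment-emergent status".

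SAP 3.7.1 gives the definition to which the imputed date is applied: "Treatment-emergent adverse events (TEAEs) are defined as AEs that start after the first dose of study drug". SAP 3.1.1 sets the day of first dose as Day 1.

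Neither document has an exception for partial dates in the month or year of first dose, a check against the stop date, or a default to treatment-emergent when timing is unclear. The statement in 3.1.6 that safety data are not imputed comes under Non-Date Values and does not apply here. SAP Section 5 (changes from the protocol) does not mention the matter.

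**The concern.** For TEAE counting, the cautious treatment of an event of uncertain timing is to keep it in the TEAE tables. The start-date rule moves it out, even when the known parts of the date fit onset under treatment. For missing days it acts only in the month of first dose, so it removes events from the first weeks of dosing.

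Safety and tolerability is a stated secondary objective, and AE incidence is a safety endpoint. The outputs affected are:

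- the TEAE-based rows of the 3.7.1 overview: all TEAEs, drug-related TEAEs, treatment-emergent SAEs, TEAEs leading to discontinuation of study drug, and TEAEs of special interest;
- the system organ class and preferred term tables built on those rows;
- the dedicated listings: "Listings will be presented specifically for TEAEs, TESAEs, TEAEs leading to discontinuation of study drug, and TEAEs of special interest".

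Several outputs are not affected. The AEs-leading-to-death row is not restricted to TEAEs, and the liver, CK and eGFR summaries in 3.7.6 rest on laboratory values. The diabetes and macular degeneration summaries carry no TEAE restriction as written: "Cases of NODM will be recorded and summarized using the appropriate system organ class" and "Cases of macular degeneration will be recorded and summarized using the appropriate system organ class". General listings show dates as collected.

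**Working it through.** The plan states no figure on this point, so there is none to reproduce.

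**Logic.** Let F be the first-dose date.

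- Day missing, month known and equal to the month of F: the imputed start is the 1st of that month, which is never later than F.
- Day and month missing, year known and equal to the year of F: the imputed start is 1 January, which is never later than F.
- SAP 3.7.1 needs a start later than F, so neither pattern can give a TEAE.

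Example: first dose 10 June, AE on 20 June. With the day missing, the imputed start is 1 June; with day and month missing, 1 January. Neither is a TEAE. An AE on 20 July with the day missing is imputed to 1 July and stays a TEAE, so missing-day AEs in later months are handled correctly.

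**Size, day missing.** Inputs from the documents: last dose on Day 56, last visit on Day 84. Assumptions not in the documents: first dose equally likely on each of 365 days, and onset uniform by day. Onsets are counted from Day 2.

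With first dose on day d of a month of L days, L - d later days remain in that month. Summed over d, this gives L(L - 1)/2:

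- seven months of 31 days: 7 × 465 = 3,255
- four months of 30 days: 4 × 435 = 1,740
- one month of 28 days: 378
- total: 5,373 pairs of first-dose date and onset date

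All 5,373 are imputed to on or before first dose. A tie arises only when first dose is on the 1st: 7 × 30 + 4 × 29 + 27 = 353 pairs (6.6%). The other 5,020 (93.4%) are imputed to strictly before first dose. For Days 2-14 and 2-28 the window cuts some pairs off, and the counts come from enumeration.

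| Onset window | Pairs | Lose TEAE status | Share | Share if a tie counts as a TEAE |
|---|---|---|---|---|
| Days 2-14 | 13 × 365 = 4,745 | 3,653 | 77% | 3,497/4,745 = 74% |
| Days 2-28 | 27 × 365 = 9,855 | 5,319 | 54% | 4,995/9,855 = 51% |
| Days 2-56 | 55 × 365 = 20,075 | 5,373 | 27% | 5,020/20,075 = 25% |
| Days 2-84 | 83 × 365 = 30,295 | 5,373 | 18% | 5,020/30,295 = 17% |
| Days 32-84 | 53 × 365 = 19,345 | 0 | 0% | 0% |

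These are shares of post-dose AEs with a missing start day, not of all AEs. They depend heavily on the calendar date of first dose: 0% to 100% for the first two windows, 0% to 30/55 = 55% for Days 2-56, and 0% to 30/83 = 36% for Days 2-84.

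**Day and month missing.** For Days 2-84, 26,809 of the 30,295 pairs have onset in the year of first dose. All 26,809 are imputed to on or before first dose. If only the month is missing and the day is known, 1,287 of 26,809 (4.8%) stay TEAEs, all with a January first dose.

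**Cost of the alternative.** If such AEs are counted as treatment-emergent unless known information excludes it, no post-dose AE in these patterns is lost, but some screening AEs are gained. With onset uniform over 14 days of screening (14 × 365 = 5,110 pairs), 3,850 (75%) fall in the first-dose month. In 105 pairs (14 + 13 + ... + 1) the onset is in the previous year, so 5,005/5,110 = 98% fall in the first-dose year.

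**The case against.** Five points can be made in the plan's defence.

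- **It is only an example.** The first-of-month and January rule illustrates a broader principle, and paired with last-day and December stop dates it gives the longest duration, which is one ordinary meaning of conservative. A programmer could follow the principle instead, and the detailed programming specifications (SAP Section 6) are a separate document. However, this is the only operational start-date rule in the SAP, and treatment-emergent status is its named use. If the principle should override the example, the SAP has to say so.
- **Few dates will be partial.** AEs are assessed at each visit (Protocol 8.1), missing data are queried (Protocol 10.1.5), and follow-up ends at Day 84. This stands. An unknown month should be rarer still.
- **No inference is at stake.** SAP 3.7 makes safety descriptive, and the rule is the same in every arm. This stands. The rule lowers reported TEAE incidence and does not favour one arm by design.
- **Ties depend on the reading.** For the 7% of missing-day pairs with first dose on the 1st, loss of status rests on reading the definition strictly by date. This stands, but it moves the Days 2-56 share only from 27% to 25%.
- **The alternative exchanges one error for another.** At equal daily onset rates and a full 14-day screening period, 5,373 missing-day pairs are misclassified now, against up to 3,850 under the alternative before stop dates help. The reduction is (5,373 - 3,850)/5,373 = 28% in that worst case. This also stands. The case for the change is mainly the direction of the error, and the SAP has already chosen that direction.

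**Conclusion.** The concern holds. As written, SAP 3.1.6 and 3.7.1 together class a post-dose AE as not treatment-emergent whenever its day is missing in the first-dose month, or its day and month are missing in the first-dose year. This follows from the calendar and needs no distributional assumption, apart from the ties, which rest on a strict date-level reading.

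The shares above rest on uniform onset and uniform first-dose dates. The effect on actual TEAE counts cannot be sized, because the number of partial dates is not given. It may well be small. The conclusion concerns the SAP text, since the programming specifications were not available. The wording should be corrected before database lock; the efficacy analyses are not touched.

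**What to change.** Two linked changes are needed.

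- **SAP 3.1.6.** If the known parts of an AE start date are compatible with onset on or after first dose, impute the first-dose date and classify the AE as treatment-emergent, unless a known stop date or other known date part shows onset before first dose. Otherwise keep the first-of-month and January rule.
- **SAP 3.7.1.** State that an AE whose start, recorded or imputed, equals the first-dose date counts as treatment-emergent, unless a recorded time shows onset before the dose. Without this, an AE imputed to the first-dose date would still fail the present definition.

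The cost is two or three sentences and a minor program change. The downside is that partial-date AEs from screening may be counted as TEAEs: about 75% of those with a missing day and about 98% of those with day and month missing, before stop dates are applied. This is limited to AEs starting in a screening period of up to 2 weeks, because Protocol 8.1 records conditions already present at Screening as medical history unless they later change.
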